4.2 Study Endpoints

The primary aim of this feasibility study is to evaluate if using Promogran in addition to SOC will improve the pain score compared to SOC alone. Specifically, we would like to detect a clinically meaningful difference in pain score (≥ 2 points on the pain scale) between the treatment and control arms on postoperative day (POD) 1.

Secondary aims include:

1. Describe and compare the percent of patients healed between treatment groups
2. Describe and compare weekly surface area between treatment groups
3. Compare time to complete donor site healing between treatment groups

4. Describe and compare adverse events between groups
5. Describe and compare decreased use of narcotics and other pain medications between groups
6. Describe and compare percent of granulation tissue at the donor site between treatment groups.
Granulation will be reported in quartiles (0-25%, 26-50%, 51-75%, and 76-100%).

5 STUDY ENROLLMENT AND WITHDRAWAL

Participants will be recruited from the NYU Winthrop Hospital Wound Care center, inpatient service, and other outpatient surgical services. Consent will be obtained by the principal and sub-investigators of the study.

5.1 Randomization:

Randomization will be performed 1:1 at enrollment. A computer generated randomized block assignment list will be given to the study coordinator. Each block of 2 or 4 subjects will contain an equal number of the two groups: 1) SOC, 2) Promogran+SOC. SAS PROC PLAN will be used to generate this list.

5.2 Inclusion Criteria:

1. Patient ≥ 18 years of age
2. Male or female
3. Patient scheduled to undergo STSG for any reason
4. Patient is able to provide informed consent and has read and signed the IRB-approved informed consent form.

5.3 Exclusion Criteria:

1. Active infection or history of radiation to the donor site
2. Patient has a known sensitivity to Promogran Prisma™ or silver
3. Elevated INR >3.0
4. Insensate at the donor site
5. Chronic narcotic use (>6 months of daily use)
6. Patient is currently pregnant and/or breastfeeding

The target number of enrolled patients will be 20, with 10 patients in the control and treatment groups, respectively. Patients will be allowed to withdraw consent at any time, with no adverse effect on the care received at NYU Winthrop Hospital.

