10 SOURCE DOCUMENTS AND ACCESS TO SOURCE DATA/DOCUMENTS		
.....	11	11 ETHICS/PROTECTIONI OF HUMAN
SUBJECTS.....	12	
11.1 Consent Procedures and Documentation	12	
11.2 Participant and Data Confidentiality	13	
12 DATA HANDLING AND RECORD KEEPING	13	
12.1 Study Records		
Retention	14	
12.2 Protocol Deviations	15	
14 SCHEDULE OF EVENTS.....	16	

LIST OF ABBREVIATIONS

AE	Adverse Event/Adverse Experience
CFR	Code of Federal Regulations
CRF	Case Report Form
DCC	Data Coordinating Center
DHHS	Department of Health and Human Services
DSMB	Data and Safety Monitoring Board
GCP	Good Clinical Practice
HIPAA	Health Insurance Portability and Accountability Act
ICF	Informed Consent Form
ICH	International Conference on Harmonisation

IRB	Institutional Review Board
MOP	Manual of Procedures
N	Number (typically refers to participants)
OHRP	Office for Human Research Protections
PI	Principal Investigator
POD	Postoperative day
SAE	Serious Adverse Event/Serious Adverse Experience
SOC	Standard of Care
STSG	Split Thickness Skin Graft
UP	Unanticipated Problem

Study number: s19-00437

Version: 3.2

PROTOCOL SUMMARY

Title	Impact of Promogran Prisma™ on pain of split-thickness skin graft donor sites compared to standard of care alone – a pilot study
Short Title	Impact of Prisma on donor site pain
Brief Summary	Twenty patients will be randomized into two groups: control and treatment. The control group will receive standard of care (SOC) dressings at the split thickness skin graft (STSG) donor site and the treatment group will receive Promogran in direct contact with the donor site in addition to SOC. SOC at NYU Winthrop Hospital includes, but is not limited to, xeroform or semi-occlusive adhesive dressings. The primary outcome is to assess the feasibility of evaluating Promogran in addition to SOC for the management of donor-site pain following STSG. The only difference between the two groups is the addition of Prisma in direct contact with the donor site under the SOC dressings in the treatment group.
Objectives	The primary objective of this study is to assess the feasibility of evaluating the use of a composite collagen, silver-oxidized regenerated cellulose matrix compared to the standard of care dressing on donor site pain for patients undergoing split-thickness skin grafting in preparation for a larger study.
Methodology	This is a prospective, randomized, open-label, single-center feasibility study.

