6 STUDY PROCEDURES AND SCHEDULE

The study will last six weeks. After consent and enrollment, patients in both the control and treatment groups will undergo STSG as scheduled. Promogran will be available in the operating room and applied by the operating surgeon (study or non-study surgeon) directly to the donor site of patients randomized to the treatment group. Patients in the control group will receive SOC dressings per the attending surgeon's clinical judgment. SOC dressings include a primary non-adherent dressing, a secondary gauze and transparent film or tape. The only difference between the two groups is the addition of Prisma in direct contact with the STSG donor site under the primary dressing in the treatment group.

Pain will be patient-reported using the visual analogue/Wong-Baker pain rating scale (VAS), which is reported on a scale from 0-10. Pain will be measured once at each of the following 12 time points: preoperatively, post-operatively (POD 1), and each subsequent postoperative day for ten days. After day 10, pain will be recorded by the assessing clinic provider during the weekly visits, until week six.

Patients will be followed daily while inpatient and weekly while outpatient for six weeks. The number of study visits will be between 6-10. The study visits will be combined with SOC visits and there will

be no study related procedures other than assessing pain at the donor site. Dressings will be changed and wounds assessed according to the standard of care at NYU Winthrop Hospital.

Screening Phase - Week -1 (within 7 days prior to treatment visit)

- Evaluation of eligibility for study inclusion
- Obtain informed consent
- Screening of inclusion/exclusion criteria
- Assign a unique subject identification number (SID).
- Randomize to treatment or control arm
- Perform physical examination and review medical, surgical, and medication histories.
- Perform a urine pregnancy test for females of reproductive potential.
- Collect demographic data including: date of birth, gender, race, ethnicity and tobacco use.
- Give patient pain diary and payment of \$35 patient stipend.

Treatment Phase - Day 0

- Ensure subject remains eligible prior to study product application.
- Confirm negative urine pregnancy test for females of reproductive potential prior to initial product application.
- Application of Prisma to STSG donor site for patients in the treatment group □ Record STSG donor site length and width

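### Section 5.1 gives the full block list to the site's study coordinator and prints the block sizes in an open-label trial, no allocation concealment is described, and the stated times of randomization conflict

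*Combined protocol and SAP*

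**What the plan says.** **Who holds the list.** Section 5.1: "A computer generated randomized block assignment list will be given to the study coordinator". The same paragraph names the SAS procedure that generates it and adds that "Each block of 2 or 4 subjects will contain an equal number of the two groups". The target is 20 patients, 10 per arm (end of Section 5.3).

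**Visibility of past arms.** The Methodology row of the Protocol Summary reads "This is a prospective, randomized, open-label, single-center feasibility study".

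**Who obtains consent.** The opening of Section 5 assigns this to the principal investigator and sub-investigators, not to the coordinator.

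**When randomization happens.**
- Section 5.1: "Randomization will be performed 1:1 at enrollment".
- Section 6 lists it among the screening tasks, under "Screening Phase - Week -1 (within 7 days prior to treatment visit". It follows the bullets for consent and for screening of the entry criteria.
- Section 14 marks it in the Day 0 treatment column, beside product application, and leaves the screening cell empty.

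**What depends on it.** Section 6 requires eligibility to be checked again on Day 0. Section 9.4 measures time to healing from randomization. Section 9.1 draws no inferential decision from p-values, but it calls the direction and size of the effect critical for the next trial and lists randomization among the things whose feasibility is to be determined.

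**The concern.** Section 5.1 describes how the sequence is generated, not how upcoming assignments are kept from those who decide on enrollment. It names no independent holder, envelope, central service or rule for single release. Followed as written, it lets at least one member of the site staff see every future assignment. With past arms visible and the block sizes printed, others can predict many of them.

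The unsettled timing adds to this. If patients are randomized at screening, the Day 0 eligibility check may be made with the arm known, and a late exclusion could depend on it. The healing clock would also start before the donor wound exists.

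No confirmatory result is at stake. What could be distorted is the postoperative day 1 difference that Section 9.1 intends to carry into the design of a larger trial. The pilot would also not show, from what is written, that a concealed procedure of the kind a full-scale trial needs is workable at this site.

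**Working it through.** The plan gives no figure to reproduce: the sample size rests on recruitment and cost (Section 9.1). Two checks apply.

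**1. Predictability of the stated block scheme**

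Inputs: 20 patients, 1:1, balanced blocks of 2 or 4 (Sections 5.1 and 5.3), and past arms visible (open-label). Section 5.1 does not say how the two sizes are mixed. Let p be the probability that a block has size 2; p is an assumption and is varied.

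*Holder of the list:* 20 of 20 assignments can be known.

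*Observer who sees past arms and knows the sizes,* always guessing the arm with more places left (one half when tied):
- Block of 2: expected correct = 1/2 + 1 = 1.5, and 1.5/2 = 75%. The second place is certain: 1/2 = 50%.
- Block of 4: expected correct = 1/2 + 2/3 + 2/3 + 1 = 2.833, and 2.833/4 = 71%. The third place is certain with probability 1/3 and the fourth always: (1/3 + 1)/4 = 33%.
- Over 20 patients this gives 15.0 correct and 10 certain (all blocks of 2), or 14.2 correct and 6.7 certain (all blocks of 4).

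For mixed sizes, exact enumeration over 20 patients gives:

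| Scheme | Guessed correctly | Certain, order of sizes unknown | Certain, order known |
|---|---|---|---|
| Ends 10:10, p = 0.25 | 72% | 18% | 36% |
| Ends 10:10, p = 0.50 | 72% | 15% | 40% |
| Ends 10:10, p = 0.75 | 73% | 11% | 44% |
| List cut at 20, p = 0.50 | 72% | 10% | 38% |

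In the rows ending 10:10, the last block is forced to size 2 when only two places remain. A list cut at 20 with p = 0.75 gives about 6% certain with the order unknown.

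Across these schemes the guess rate stays at 71-75%, against 50% by chance. The certain share does not settle on one value: it runs from about 6% (mixed sizes, order unknown) to 50% (all blocks of 2).

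**2. The stated times side by side**

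| Place | Time of randomization |
|---|---|
| Section 5.1 | At enrollment |
| Section 6 | Screening, up to 7 days before treatment |
| Section 14 | Day 0 |

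Section 14 lets screening run from Day -7 to Day 0, so all three agree only when screening falls on Day 0. That is permitted but not required. Otherwise the gap is up to 7 days, with two consequences:
- The Day 0 eligibility check in Section 6 follows allocation.
- Under Section 9.4 the healing clock starts up to 7 days before the graft is harvested, by an amount that varies between patients.

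**The case against.** **Roles are partly separated.** Investigators obtain consent and the coordinator holds the list. Steering who is enrolled next would then need either disclosure by the coordinator or a coordinator role in recruitment, and the documents state neither. This stands as a limit on the all-20 figure. It is not concealment: nothing says the list is withheld from investigators, or that the coordinator takes no part in screening or scheduling.

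**Silence is not absence.** A reader might infer that the pilot was run without concealment. The documents do not support that. Section 12.2 refers to a Manual of Procedures that was not available, and neither was the continuation of the study schematic. Only non-description is established.

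**Mixed block sizes give some protection.** True for certainty: with the order unknown, the certain share falls well below the fixed-block values. The guess rate barely moves.

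**Order of the screening tasks.** A reader might infer that patients are randomized before exclusions such as "Patient is currently pregnant and/or breastfeeding" can be checked, because Section 6 lists the history review and pregnancy test after randomization. That reading is weak. The bullets need not be in time order, and screening of the entry criteria is listed before randomization. The point does not rest on it.

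**It is a small pilot.** With no decision based on p-values, the consequence is limited. That bears on priority, but Section 9.1 still gives the effect estimate and the feasibility of randomization a purpose.

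**Conclusion.** The concern holds as a gap in the written procedure plus a contradiction in timing. The contradiction is the firmer part, because it stands on the face of Sections 5.1, 6 and 14. Concealment is not described, and the procedure as written permits foreknowledge of up to 20 of 20 assignments by a list holder. It permits a guess rate of about 71-75% by anyone tracking past arms. The certain share of about 6% to 50% depends on assumptions about the block mix, the end of the list and knowledge of the order of sizes, so no single value in that range should be quoted as the result.

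A reader might go further and conclude that the postoperative day 1 pain difference is biased. The documents do not allow that: the bias in pain points cannot be derived, and it is zero if nobody acts on the knowledge. The change is worth making before enrollment because it costs little, but the gap does not by itself invalidate the pilot.

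**What to change.** 1. **Section 5.1.** Replace the sentences on the list and block sizes with text to this effect: The list is generated and held by someone with no role in recruitment or assessment, such as the study statistician. Assignments are released one at a time, by sequentially numbered opaque sealed envelopes or an access-restricted system that the recruiting team does not control. Release follows only after consent and confirmed eligibility are recorded and the enrollment entry is logged and cannot be reversed; the participant's right to withdraw is unaffected. Block sizes are kept in a restricted document. If the Manual of Procedures already provides this, cite it here instead.

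2. **Sections 5.1, 6 and 14.** State one time of randomization in all three places, after the final eligibility check and as late as practicable before product application. This also limits how far the healing clock in Section 9.4 can run ahead of the wound.

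**Cost.** No extra patients, and no extra staff if the statistician holds the list. The burden is logistic: the assignment must reach the operating room in time, including when a non-study surgeon applies the product (Section 6). A module in the existing database would need restricted access, since Section 12 places that database with the Wound Care team. Some guessing from past arms will remain because the trial is open-label.

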Endpoint	The primary endpoint of this feasibility study is to evaluate if using Promogran in addition to SOC is associated with a clinically meaningful difference in pain score (≥ 2 points on the visual analog pain scale) between the treatment and control arms on postoperative day (POD) 1.
Study Duration	Two years
Participant Duration	Six weeks
Duration of IP administration	One application
Population	Twenty patients; 10 in the intervention group and 10 in the control group. All genders, ≥ 18 years old, all demographics and geographic locations; scheduled to undergo STSG.
Study Sites	Single site: NYU Winthrop Hospital
Number of participants	20 participants
Study compensation	\$70. Two payments of \$35 will be given to participants – one at enrollment and one at collection of the 10-day pain diary.
Description of Study Agent/Procedure	Promogran Prisma™ is a composite collagen-silver-oxidized regenerated cellulose dressing that is a sheet applied topically to the STSG donor site.
Reference Therapy	The control group will receive a standard of care dressing on the STSG donor site (i.e., non-adherent dressing)
Key Procedures	Placement of either Prisma or standard of care dressing on the STSG donor site. Record daily pain score of the donor site for 10 days post-grafting. Return to clinic for weekly follow-up visits for 6 weeks.

Statistical Analysis	Proposed sample size (10 patients in each arm, a total of N=20) is obtained from a recruitment and cost feasibility point of view. For the primary endpoint, the pain score at POD 1 will be compared between treatment groups using Wilcoxon rank-sum (Mann-Whitney) test. The secondary endpoint, time from randomization to donor site healing, will be compared between treatment groups using time to event approach via Kaplan-Meier method.
----------------------	--

SCHEMATIC OF STUDY DESIGN

Total 20: Obtain informed consent. Screen potential subjects by inclusion and exclusion criteria. Perform physical examination and review medical, surgical, and medication histories. Perform a urine pregnancy test for females of reproductive potential. Collect (Day -7 - 0) demographic data including: date of birth, gender, race, ethnicity and tobacco use.

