2.1 Background Information and Relevant Literature

Split-thickness skin grafting (STSG) is the mainstay of therapy for the management of wounds that cannot be closed primarily or left open to close by secondary intention. However, the wounds created by STSG are often a source of pain and morbidity to patients. Multiple studies have compared various donor site dressings in attempt to decrease pain and morbidity¹⁻⁴. This study will look specifically at the effect on patient-reported donor site by using of a collagen dressing. The addition of a composite collagen-silver-oxidized regenerated cellulose dressing (Promogran Prisma™) which has been cleared by the FDA(510k) in direct contact with the donor site is hypothesized to decrease pain at the donor site.

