3 RESEARCH OBJECTIVES AND PURPOSE OF THE STUDY

The primary purpose of this study is to assess the feasibility of evaluating the use of a composite collagen, silver-oxidized regenerated cellulose matrix compared to the standard of care dressing on donor site pain for patients undergoing split-thickness skin grafting in preparation for a larger study.

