7.6 Reporting Procedures – Notifying the Study Sponsor

The study clinician will complete a SAE Form within the following timelines:

- All deaths and immediately life-threatening events, whether related or unrelated, will be recorded on the SAE Form and submitted to the DCC/study sponsor within 24 hours of site awareness. See Section 1, Key Roles for contact information.
- Other SAEs regardless of relationship will be submitted to the DCC/study sponsor within 72 hours of site awareness.

All SAEs will be followed until satisfactory resolution or until the site investigator deems the event to be chronic or the adherence to be stable. Other supporting documentation of the event may be requested by the DCC/study sponsor and should be provided as soon as possible.

As a follow-up to the initial report, within the following 48 hours of awareness of the event, the investigator shall provide further information, as applicable, on the unanticipated event or the unanticipated problem in the form of a written narrative. This should include a copy of the completed Unanticipated Problem form, and any other diagnostic information that will assist the understanding of the event. Significant new information on ongoing unanticipated adverse effects shall be provided promptly to the study sponsor.

8 Clinical Monitoring

Clinical site monitoring will be conducted to ensure that the rights and well-being of human subjects are protected, that the reported trial data are accurate, complete, and verifiable, and that the conduct of the trial is in compliance with the currently approved protocol/amendment(s), with Good Clinical Practice (GCP), and with applicable regulatory requirement(s).

Data safety monitoring will be done by the Clinical Research Coordinator. Events that will be monitored are infection at donor site, increasing pain at donor site, and allergic reaction to dressing. Monitoring will occur on a weekly basis once patients are enrolled. There are no predefined stopping points and reviews will be disseminated at the weekly research meeting.

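### Exclusion criterion 2 names the product and silver but not collagen or oxidized regenerated cellulose, so a known sensitivity to either meets no written exclusion

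*Combined protocol and SAP*

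**What the plan says.** **Product.** The Protocol Summary (Description of Study Agent/Procedure) states: "Promogran Prisma™ is a composite collagen-silver-oxidized regenerated cellulose dressing that is a sheet applied topically to the STSG donor site". Section 2.1 gives the same composition: "The addition of a composite collagen-silver-oxidized regenerated cellulose dressing (Promogran Prisma™". Section 3 names the same materials, punctuated differently: "composite collagen, silver-oxidized regenerated cellulose matrix".

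**Who is kept out.** The only exclusion in section 5.3 that concerns allergy is criterion 2: "Patient has a known sensitivity to Promogran Prisma™ or silver". It has no wording that extends it to the product's other ingredients.

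**Who is let in.** Inclusion is broad. Section 5.2 accepts adults who can consent and meet "Patient scheduled to undergo STSG for any reason". No inclusion criterion concerns allergy.

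**Exposure.** Under section 6 the operating surgeon applies the sheet "directly to the donor site of patients randomized to the treatment group". The control arm does not receive it. Section 5.1 allocates 1:1.

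**Later checks.** Section 6 includes a review of medical, surgical and medication histories at screening. On Day 0 it adds the step "Ensure subject remains eligible prior to study product application".

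**Monitoring.** Section 8 states: "Events that will be monitored are infection at donor site, increasing pain at donor site, and allergic reaction to dressing".

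**The concern.** A patient who has never used the product will usually have no known sensitivity to it by name. For that patient, the practical screening is done by whatever components the criterion lists, and it lists only silver. Someone with a documented sensitivity to collagen or oxidized regenerated cellulose can therefore pass every written criterion.

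What is at stake is an avoidable exposure, in the treatment arm only, of a patient whose sensitivity was already known. The plan itself treats allergy as important: it has an allergy exclusion, and allergic reaction to the dressing is one of only three events singled out for safety monitoring in section 8. The exclusion does not carry that intent through to the composition the protocol states.

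**Working it through.** The plan gives no figure on this point, so the check sets the passages side by side.

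**Step 1. Components stated against components named.**

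| Component | Protocol Summary, sections 2.1 and 3 | Section 5.3, criterion 2 |
|---|---|---|
| Silver | stated | named |
| Collagen | stated | not named |
| Oxidized regenerated cellulose | stated | not named |

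Count: 3 stated, 1 named, 3 − 1 = 2 not named. The punctuation in section 3 could be taken to join silver and cellulose into one material. That does not change the result, because collagen and the cellulose are still not named in the criterion.

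**Step 2. Could the product name cover its ingredients?** There are two ways to read criterion 2.

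- Broad: sensitivity to the product includes sensitivity to anything in it. Silver would then already be covered, and naming it would be redundant.
- Narrow: the product name means a known reaction to the product. Naming silver then does real work, and collagen and oxidized regenerated cellulose are left out.

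The separate mention of silver favours the narrow reading. It does not rule out the broad one.

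**Step 3. Does another criterion cover it?** The other five exclusions concern infection or radiation at the donor site, INR, an insensate donor site, chronic narcotic use, and pregnancy or breastfeeding. None concerns allergy. Nor do the four inclusion criteria.

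**Step 4. Does a later step cover it?**

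- The history review may bring a documented allergy to light, but no rule links a collagen or cellulose sensitivity to exclusion.
- The Day 0 step re-applies the same criteria. A patient who passed them as written still passes.
- Section 2.2 lists allergic reaction as a risk, section 7.2 as an example of an adverse event, and section 8 as a monitored event. These disclose or detect a reaction; they do not prevent the exposure.

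**Step 5. What follows for one such patient.** With 1:1 allocation, a patient enrolled under the literal reading has a 1/2 = 50% chance of assignment to the sheet. How many such patients to expect among 20 depends on a prevalence that the documents do not give, so no expected count is calculated.

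**The case against.** **The product name may be enough.** The protocol defines the product by its components. An investigator who sees a documented collagen allergy could reasonably treat it as a sensitivity to a collagen dressing. This stands in part. It means the patient may be read as eligible, not that every site clinician would enrol them. It does not remove the gap, because the text does not say so and the separate mention of silver points the other way.

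**Clinicians are a safeguard.** Histories are reviewed at screening, a surgeon applies the sheet, and section 11 says the consent form describes the study agent in detail. The consent pages are not part of the text available here, so their allergy wording cannot be judged. These steps make an actual exposure less likely, but none is a written eligibility rule.

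**There is no contradiction.** An exclusion that names the product and one component does not conflict with the product description. That is correct. The finding is incomplete coverage, not two statements that cannot both be true.

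**The effect on the results is speculative.** A reader might infer that one such patient would distort the pain comparison. The documents do not support this. The POD 1 comparison in section 9.3 is rank-based, which limits one patient's influence, and section 9.1 says no inferential decision will rest on p-values. Moreover, a known sensitivity is not the same as a reaction, and no reaction probability is given. This part of the objection stands in full.

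**Conclusion.** The gap is real on the text: two of the product's three stated components are missing from the only allergy exclusion, and no other criterion or check covers them. The conclusion rests on a literal reading of criterion 2, for a patient with no known reaction to the product itself. It means eligibility for enrolment with a 1:1 chance of assignment to the sheet, not certain exposure.

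A reader might want to attach a probability that a sensitive patient is among the 10 treated. The documents give nothing to anchor one, and any figure would reflect only the prevalence assumed. One patient is 1/10 = 10% of the treatment arm, but that describes the size of the arm and is not a forecast of reactions.

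The point concerns participant safety and the clarity of the eligibility rule. It has no bearing on the sample size, the error rates or the choice of test. It is worth correcting because the change is small and the exposure is avoidable.

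**What to change.** The sponsor and investigator should reconcile exclusion criterion 2 in section 5.3 with the composition stated in the Protocol Summary and section 2.1, so that the sensitivity exclusion addresses all stated components. The same criterion should apply to every candidate before randomization, whichever arm follows, so that the two arms are drawn from the same population. The relevant allergy history therefore has to be in hand by then. Section 6 lists the history review after randomization; if that list is meant as a sequence, the order should be clarified.

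The cost is one phrase in section 5.3 and the usual approval of an amendment by the IRB (section 11). The downside is the possible loss of a rare candidate from a target of 20. No change to the statistical analysis is needed.
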